#### **5.4.6.2. Analysis of Adverse Events**

The number and percentage of participants with at least one particular AE will be tabulated with exact 95% CI, when appropriate. Additionally the incidence rate will also be derived as number of participants with at least one particular AE per 100 person years of follow-up. Unsolicited AEs will be summarized by System Organ Class and Preferred Term.

Denominator for the percentages is the number of participants in the considered population and phase for a certain vaccination group (incidence per 100 participants/phase). Denominator for the incidence rates is the number of person years in the considered population and phase for a certain vaccination group (incidence per 100 person years/phase).

For unsolicited AEs, the following tables will be provided: summary table (including SAEs, SAEs related to study vaccine, MAAEs, MAAEs leading to study discontinuation, MAAEs related to study vaccine, AEs with fatal outcome, AEs related to study vaccine with fatal outcome, AEs related to study vaccine leading to study discontinuation, and AEs leading to study discontinuation), all events, AEs at least grade 3, AEs related to study vaccination, AEs at least grade 3 and related to study vaccination, AEs leading to study discontinuation, SAEs related to study vaccination, SAE (overall, associated with COVID, not associated with COVID), MAAE, selected AEs of interest, fatal AEs, and AESI.

Listings and/or participant narratives will be provided as appropriate, for those participants who die, discontinue study due to an AE, or experience a serious AE.

### 5.4.6.3. Phase Allocation of Adverse Events

#### Step 1: Allocation of events to the periods:

Adverse events in the study data tabulation model (SDTM) database are allocated to periods based on their start date/time. If the start date/time of an event falls between (or on) the start and stop date/time of a period, the AE is attributed to that period (treatment-emergent principle).

- In case of partial start or stop dates (ie time and/or day and/or month and/or year missing), the events are allocated to the periods using the available partial information on start and end date; no imputation will be done. If, for instance, for the AE start date only month and year are available, these data are compared to the month and year information of the periods. This rule may lead to multiplication of the event as a consequence of its assignment to multiple periods.
- In case of a completely missing end date, the date is imputed by the cut-off date of the analysis for participants still ongoing in the study, and by the end date of the last period for participants who discontinued or completed the study. In case of a completely missing start date, the event is allocated to the first active treatment phase (post dose period 1), except if the end date of the AE falls before the start of the first active treatment phase (post dose period 1).

#### Step 2: Combination of events:

Overlapping/consecutive events are defined as events of the same participant with the same preferred term which have at least 1 day overlap or for which the start date of an event is 1 day after the end date of the preceding event. Overlapping/consecutive events may be combined into one AE or not, according to the following rules:

1. If overlapping/consecutive events start in one of the following periods - Screening or post dose extension (ie non-active periods) - followed by an AE in - post-dose period (active period) - they are allocated to their respective periods and are considered as separate events.
2. In case overlapping/consecutive events start within a single period, they are considered as one and the same AE. The individual events which contribute to this AE are retained as individual records in the Analysis Data Model (ADaM) database but are assigned the same onset, period, and total duration. All related attributes to the AE/phase/period should also be consistent with the new event.
3. In case overlapping/consecutive events start in both an active period followed by a non-active period, they are allocated to the active period only and are considered as one and the same AE. The individual events which contribute to this AE are retained as individual records in the ADaM database but are assigned the same onset, treatment period, and total duration. All related attributes to the AE/phase/period should also be consistent with the new event.
4. In case an active period is followed by another active period, and the overlapping/consecutive events start in both periods, they are allocated to their respective period and are considered as separate AEs. The same rule applies for 2 non-active periods.

Remarks:

1. Events can only be combined into one and the same AE if their start and stop dates are known.

2. In case the completely missing end date is imputed (for period allocation), this date is also considered as a complete date.
3. Time is not considered when determining overlap of events.

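### An adverse event with no end date can pull a later follow-up event of the same term, serious or fatal ones included, back into an earlier post-dose period

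*SAP*

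**What the plan says.** SAP 5.4.6.3 works in two steps.

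**Step 1** allocates each AE to a period by its start date. Partial dates are not imputed. A completely missing end date is: "the date is imputed by the cut-off date of the analysis for participants still ongoing in the study". Where a participant has already left or finished, the close of that person's final period is used instead.

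**Step 2** combines overlapping or consecutive events, defined as "events of the same participant with the same preferred term which have at least 1 day overlap", or records on consecutive days.

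- Rule 1 (non-active, then active period): "they are allocated to their respective periods and are considered as separate events".
- Rule 2 (both start in one period): merged, with no change of period.
- Rule 3 (active, then non-active period): "they are allocated to the active period only and are considered as one and the same AE". The records share onset, period and total duration, and related attributes are to be made consistent.
- Rule 4 (active then active, or non-active then non-active): kept separate.

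Remark 1 restricts merging: "Events can only be combined into one and the same AE if their start and stop dates are known". Remark 2 then admits the imputed date: "In case the completely missing end date is imputed (for period allocation), this date is also considered as a complete date".

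In Table 6 the post-dose period runs from vaccination to 28 days later, or to the next vaccination if earlier. Under 5.4.4, layouts 1a and 1b are tabulated by phase and period. Under 5.4.6.2, percentages and rates count participants with at least one event, over phase-specific denominators.

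**The concern.** An end date that nobody recorded decides whether two records are one event and when that event began. The assumed date is the latest one possible, so it creates an overlap with every later record of the same term, however long the gap. Rule 3 then overrides the Step 1 allocation by recorded start date.

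Treatment of incomplete dates is also uneven. On the natural reading, an AE with a partial end date cannot be merged, because partial dates are not imputed and Remark 1 requires known dates. An AE with no end date at all can be merged.

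At stake is the timing of later events relative to vaccination. The safety output of this plan is largely phase-specific counts and rates, and Rule 3 has no exception for serious or fatal AEs. Its wording also does not say that the non-active period must be the follow-up of the same vaccination.

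**Working it through.** **1. Which pairs of periods are affected?** Take two records of the same term, the first with no end date, so that it overlaps any later one. Apply Rules 1 to 4 to every ordered pair of start periods in two illustrative participants: (a) Ad26.COV2.S on days 0 and 56; (b) placebo on day 0 and Ad26.COV2.S on day 120. The day-120 cross-over is an assumption and does not affect the rule outcomes. Rule 1's post dose extension is read as the Table 6 follow-up phases. Each participant has 6 periods, so 6 × 7 / 2 = 21 pairs: 6 within one period and 15 across periods.

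| Outcome | Rule | Pairs in (a) | Pairs in (b) |
|---|---|---|---|
| Same period, merged, no shift | 2 | 6 | 6 |
| Kept separate | 1 and 4 | 10 | 10 |
| Merged and moved back to a post-dose period | 3 | 5 | 5 |

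The 5 Rule 3 pairs divide as follows:

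- 2 are a post-dose period and the D30-M6 follow-up directly after it. These shift on any reading.
- 1 is the M6-End follow-up of the same dose. It shifts only if Rule 3 covers any later non-active period.
- 2 cross a vaccination, and depend on that same wide reading: follow-up 2 to post-dose 1 in (a), and Ad26.COV2.S follow-up to placebo post-dose in (b).

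A later record that starts inside another dose's post-dose period is never moved. A first record that starts in screening or follow-up never pulls a later one out of its own period.

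**2. Example on the narrowest reading.** A mild AE starts 5 days after a dose and has no end date. An SAE of the same term starts in the D30-M6 follow-up of that dose. Step 1 places the SAE in follow-up. The imputed end date creates the overlap, Remark 2 satisfies Remark 1, and Rule 3 gives the SAE the onset and period of the mild AE.

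**3. Effect on the tables.** Under 5.4.6.2 participants are counted once.

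- Follow-up rows: the participant drops out, unless another qualifying record remains.
- Post-dose all-AE row for that term: no change, since the first record already counts.
- Post-dose AEI rows (Appendix 6) and programmatically selected AESI rows (5.4.6.1): no change, since selection is by MedDRA term and the first record already qualifies.
- Post-dose serious, grade 3, related or fatal rows: one participant is added if only the later record has that attribute and it carries to the merged AE. Step 2 does not name seriousness, grade or relatedness among the shared items, so this is open.

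**4. Size per event where the attribute carries over.** Assume 30,000 participants and a 29-day window (day of vaccination plus 28 days).

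- Post-dose person-years (PY) = 30,000 × 29 / 365.25 = 2,382. One event adds 100 / 2,382 = 0.042 per 100 PY.
- Assumed follow-up phases of 0.5, 1.0 and 1.5 years give 15,000, 30,000 and 45,000 PY. One event removes 0.0067, 0.0033 and 0.0022 per 100 PY.
- Ratios: 6.3, 12.6 and 18.9. These reflect only the lengths of the windows.

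The SAP gives no count of AEs without an end date, so no total can be computed.

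**The case against.** Remarks 1 and 2 need not conflict: the second says which imputed dates count as known. Treating an AE without an end date as ongoing is a common convention, and a new record of the same term may be a worsening of the same event. This stands for period allocation. It does not justify re-dating a separately recorded serious event to the onset of a mild one.

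A reader might infer that any later event of the same term is merged. The text does not support that: Rules 1 and 4 keep 10 of the 15 cross-period pairs separate.

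A reader might also infer that the plan moves Ad26.COV2.S events to placebo, or from one dose to another. That needs Rule 3 to cover any later non-active period. Immediate succession is a natural reading, and Rule 4 uses the same construction. The placebo shift would also contradict 5.4.4, where placebo data stop at the first active vaccination, and 5.4.8, which censors placebo follow-up there. What remains is that Rule 3 does not exclude these shifts. Nor does it say which period receives a third record when same-term events start in post-dose 1, post-dose 2 and follow-up 2.

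Counting participants once removes any inflation of the same-term all-AE post-dose rows. This objection stands in full, and merging of recurrences within one period likewise leaves those counts unchanged.

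Finally, individual records stay in ADaM, listings or narratives are planned as appropriate for deaths and serious AEs, a whole-study summary covers Ad26.COV2.S recipients, and safety is descriptive. These help to trace an event but do not correct the phase tables. The term post dose extension is glossed as non-active, so that part is editorial.

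**Conclusion.** The point holds in a limited form. As written, Remark 2 and Rule 3 together take a later same-term follow-up event out of the phase in which it occurred and date it to an earlier post-dose period, serious and fatal events included. Between a post-dose period and the D30-M6 follow-up directly after it, this needs no special reading of the rules.

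The certain effect is loss from the follow-up tables. Gain in the post-dose tables is conditional on an attribute that only the later record has and that carries to the merged AE. In that case one event is worth 0.042 per 100 PY on the assumed 30,000 participants, and for same-term all-AE rows the gain is zero. Shifts across doses or to placebo are a gap in the wording, not a stated rule. With no count of AEs lacking an end date, the overall effect is unknown and no material distortion has been shown. The case for acting is that the rule can misplace serious events in time and is cheap to correct.

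**What to change.** In SAP 5.4.6.3:

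1. Replace Remark 2 by a statement that imputed end dates serve period allocation only and are not used to combine events.
2. Limit Rule 3 to the follow-up of the same vaccination within the same vaccination group.
3. Tabulate SAEs and fatal AEs by phase on their own recorded start date.
4. Replace post dose extension in Rule 1 by the Table 6 follow-up phases.

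The general statement in 5.4.6.4 that missing data are not imputed should also note the end-date exception in Step 1.

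The cost is SAP wording and a small change to the ADaM derivation. The downside is that a few truly continuous events will be counted in two phases; a table footnote can say so.

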#### **5.4.6.4. Missing Data**

Missing data will not be imputed. Participants who do not report an event/concomitant medication will be considered as participants without an event/concomitant medication. An AE with a missing severity or relationship will be considered as an AE reported, but will be considered as not reported for the severity or relationship. For example, an AE with missing severity will be considered as an AE reported for the analysis of any grade, but will be considered as not reported for the analysis of at least grade 3.

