**Table 6: Phase Definitions for Safety Analysis**

Phase	Phase #	Period	Period #	Interval	
				From	To
Screening	1			Date and time of signing the informed consent form	One minute prior to start of post dose 1 period
Post Dose	2	Post dose 1	1	Date and time of first vaccination	
Minimum of
 
 
a) 23:59 at the date of last contact (for early discontinuation or completion)
 
b) 23:59 at the date of database cut-off date
 
c) 23:59 on 28 days after the first vaccination (23:59 of day of vaccination + 28 days)
 
d) One minute prior to date and time of next vaccination
 

Follow-up 1 (D30-M6)	3			One minute after post-dose 1 period ends	
Minimum of:
 
 
a) 23:59 at the date of last contact (for early discontinuation or completion)
 
b) 23:59 at the date of database cut-off date
 
c) 23:59 at the date of Month 6 (date of vaccination + 6 months)
 
d) One minute prior to date and time of next vaccination
 

Follow-up 1 (M6-End)	4			One minute after follow-up 1 (D30-M6) ends	
Minimum of:
 
 
a) 23:59 at the date of database cut-off
 
b) One minute prior to date and time of next vaccination
 
c) maximum of: 
 
1. 23:59 at the date of last contact (for early discontinuation or completion)
 
2. 23:59 at the date of last visit (for completion )
 
 
 

Post Dose	2	Post dose 2	2	Date and time of second vaccination	
Minimum of
 
 
a) 23:59 at the date of last contact (for early discontinuation or completion)
 
b) 23:59 at the date of database cut-off date
 
c) 23:59 on 28 days after the second vaccination (23:59 of day of vaccination + 28 days)
 
d) One minute prior to date and time of next vaccination
 

Follow-up 2 (D30-M6)	5			One minute after post-dose 2 period ends	
Minimum of:
 
 
a) 23:59 at the date of last contact (for early discontinuation or completion)
 
b) 23:59 at the date of database cut-off date
 
c) 23:59 at the date of Month 6 (date of vaccination + 6 months)
 
d) One minute prior to date and time of next vaccination
 

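### AEs with missing severity or relationship drop out of the grade 3+ and related counts, which can therefore only be understated, and no worst-case count is planned

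*SAP*

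**What the plan says.** **Missing attributes.** SAP section 5.4.6.4 states that missing data are not imputed. An AE with missing severity or relationship "will be considered as an AE reported, but will be considered as not reported for the severity or relationship". The section's own example is an AE with no grade: it counts in the any-grade analysis but "will be considered as not reported for the analysis of at least grade 3".

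**Tables affected.** Section 5.4.6.2 lists, among others, "AEs at least grade 3, AEs related to study vaccination, AEs at least grade 3 and related to study vaccination". Its summary table adds further rows defined by relationship: related SAEs, related MAAEs, related fatal AEs and related AEs leading to discontinuation.

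**Missing start dates.** Section 5.4.6.3, Step 1, has two rules.
- Completely missing date: "In case of a completely missing start date, the event is allocated to the first active treatment phase (post dose period 1"). The one exception is an AE known to have ended before that period began.
- Partial date: the AE goes to every period that matches the available information. The SAP notes: "This rule may lead to multiplication of the event as a consequence of its assignment to multiple periods".

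**The concern.** A missing grade or causality assessment carries no information, yet the tables treat it as if the AE were below grade 3 or unrelated. The error can run only one way. Related SAEs and related deaths are likely to be few, so one or two unassessed events could change a row. A reader of the table could not tell a true zero from a zero that rests on blank fields, because section 5.4.6.4 asks for neither a worst-case count nor the number of missing values.

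The start-date rule raises a separate and smaller question. A participant who had placebo or an outside vaccine before Ad26.COV2.S can have two periods that may be called post-dose 1. Depending on which one is meant, the same undated AE is reported under a different vaccination group.

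**Working it through.** **1. Missing severity or relationship**

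The SAP gives no missingness rate and no expected share of related or severe AEs, so there is no planned figure to reproduce. Both inputs below are assumptions:
- *s*: share of AEs with a recorded value that are related (or at least grade 3)
- *m*: share of all AEs with that value missing

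Formulas:
- Reported under the SAP: s(1 − m)
- If values are missing at random: s
- Worst case (every missing value is related or grade 3+): s(1 − m) + m
- Shortfall relative to missing at random: 1 − s(1 − m)/s = m
- Shortfall relative to the worst case: m / [s(1 − m) + m]

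Worked example, s = 10% and m = 2%: reported 0.10 × 0.98 = 9.8%; worst case 9.8% + 2% = 11.8%; shortfall against the worst case 2/11.8 = 16.9%.

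| s | m | Reported | Worst case | Shortfall vs missing at random | Shortfall vs worst case |
|---|---|---|---|---|---|
| 10% | 0.5% | 9.95% | 10.45% | 0.5% | 4.8% |
| 10% | 1% | 9.90% | 10.90% | 1% | 9.2% |
| 10% | 2% | 9.80% | 11.80% | 2% | 16.9% |
| 10% | 5% | 9.50% | 14.50% | 5% | 34.5% |
| 2% | 0.5% | 1.99% | 2.49% | 0.5% | 20.1% |
| 2% | 1% | 1.98% | 2.98% | 1% | 33.6% |
| 2% | 2% | 1.96% | 3.96% | 2% | 50.5% |
| 2% | 5% | 1.90% | 6.90% | 5% | 72.5% |

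The gap to the worst case is always m percentage points, so it weighs most on rare categories. If values are missing at random, the relative loss is only m. These are shares of AEs. Section 5.4.6.2 counts participants with at least one such AE, so a participant with another qualifying AE in the same row is not lost.

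On direction between groups: if *m* is the same in two groups and values are missing at random, the ratio of reported shares is s₁(1 − m) / [s₀(1 − m)] = s₁/s₀, which is unchanged. If *m* differs between groups, the direction depends on rates that the SAP does not give.

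**2. Completely missing start date**

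No arithmetic applies. The relevant texts, side by side:
- Table 6 starts post-dose 1 at the first vaccination and ends it no later than "23:59 on 28 days after the first vaccination".
- The text after Table 6 in section 5.4.3 gives placebo-first participants separate post-dose periods for the placebo and the active injections. On Table 6 numbering, their post-dose 1 is therefore the placebo period.
- The same section restarts the numbering at 1, for reporting, when Ad26.COV2.S follows placebo only, or only mRNA or only non-mRNA outside vaccines. On that numbering, post-dose 1 is the Ad26.COV2.S period.
- The word active does not settle it. Section 5.4.4 uses it for Ad26.COV2.S or an outside vaccine, whereas Step 2 of section 5.4.6.3 uses it for post-dose periods in general, as opposed to screening.

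For a placebo-first participant who crossed over, an undated AE can thus fall under placebo or under Ad26.COV2.S. For an outside-first participant it can fall in the mixed-schedule group (layout 2) or in the group given Ad26.COV2.S after an outside vaccine (layout 1b).

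**The case against.** The strongest reply is that little of importance depends on this rule.
- The safety estimands in section 1.1 are SAEs, AEIs and AESIs, none of them defined by grade or relationship.
- Section 5.4.6.2 tabulates all SAEs and all fatal AEs regardless of causality, and provides listings or narratives, as appropriate, for deaths, SAEs and discontinuations due to an AE. A death with blank causality remains visible.
- Safety is descriptive, with no formal testing (section 5.4).
- Not imputing is an openly stated convention. Making the worst case the main analysis would swap undercounting for overcounting.

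All of this stands. It limits the importance of the point and argues for adding a worst-case count beside the planned one. It does not remove the one-sidedness: each group's related and grade 3+ figures are reported as absolute counts and rates, and these are understated whether or not placebo is affected equally.

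A reader might go further and infer that the rules favour the vaccine. The SAP does not support that. The missing-attribute rule is the same for placebo. The start-date rule deletes no event. For a participant whose first vaccination was Ad26.COV2.S, it puts an undated AE into the window of at most 28 days after that dose and so raises the early post-vaccination count, even if an outside vaccine came later.

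A reader might also infer that undated AEs always go to the first dose. The rule covers only completely missing start dates and has an end-date exception. Partial dates go to every matching period, which can overcount later doses. For cross-over participants, the restarted numbering may already mean the Ad26.COV2.S period.

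**Conclusion.** The point holds as a minor one. Under section 5.4.6.4 the related and grade 3+ counts of section 5.4.6.2 can be understated in every vaccination group and never overstated by this rule, and no worst-case check is planned there. The size cannot be stated. It is nil with complete data. With missing values it lies between a relative loss of m (missing at random) and m percentage points (worst case), provided that AEs with missing values are at least as often related or severe as the assessed ones. All percentages shown rest on assumed s and m. The SAE, AEI and AESI estimands are unaffected.

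The start-date rule is a secondary matter of clarity: the SAP allows two readings of post-dose 1 for participants who first had placebo or an outside vaccine. It is not evidence of bias towards the vaccine.

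**What to change.** 1. **Section 5.4.6.4 and the related and grade 3+ tables of 5.4.6.2:** keep the planned counts and add a worst-case count, with missing relationship counted as related and missing grade counted as at least grade 3. In the table of "AEs at least grade 3 and related to study vaccination", include in the worst case any AE that no recorded value excludes. Footnote the number of AEs with missing severity and with missing relationship per vaccination group.
2. **Section 5.4.6.3, Step 1:** state which post-dose 1 period (Table 6 numbering or the restarted numbering) receives an AE with a completely missing start date in participants who first had placebo or an outside vaccine. List such AEs for participants with two or more vaccinations, since any allocation to a first period leaves later doses without them.

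The cost is SAP wording and a simple programming rule, with no new data. The small downside is that a few counts may look slightly less favourable. If no values are missing, no result changes.
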